8.3.6.4 Reporting of Serious Adverse Events

An AE that is serious or potentially serious requires the following additional detailed reports and follow-up and should be recorded in the CRF. The content of these detailed reports should address the Investigator's (or in some cases, the Sponsor's) estimate of causality, and whether or not the AE is identified in nature, severity, and frequency in the [Investigator's Brochure](#) or in other risk information that has been supplied to the Investigator.

Sponsor Notification

Any SAE that occurs after starting study drug administration must be reported to the Clinical Study Monitor or Project Manager as soon as information is available. In turn, the Clinical Study Monitor/Project Manager must immediately inform the Medical Monitor of the event and document the notification in a telephone/contact report. The urgency for reporting a SAE is three-fold: (1) to facilitate discussion (and implementation, if necessary) by the Sponsor and the Investigator of appropriate follow-up measures; (2) to facilitate Investigator reporting of unanticipated problems involving risk to human patients to the IRB/REB; and (3) to enable the Sponsor to fulfil the requirements to the appropriate regulatory authority.

Any non-fatal or non-life-threatening SAE, regardless of expectedness or causality, or fatal or life-threatening SAE must be immediately reported to the Clinical Study Monitor or Project Manager by telephone or facsimile, and a written report (Serious AE Report Form) signed by the Investigator must be provided to the Clinical Study Monitor or Project Manager promptly, but no later than the timelines outlined in Table . This documentation will be forwarded to the Medical Monitor immediately to facilitate the prompt detection by the Medical Monitor of any changes in the nature, severity, or frequency of serious AEs, and allow the Sponsor to meet reporting requirements of the appropriate regulatory agency.

Table 3 Serious Adverse Event Reporting Requirements for Protocol 2076-CL-006

Communication	Initial Reports		Follow-Up Reports
	Fatal or Life-Threatening SAE	Other SAEs	Any SAE
Vendor SAE Portal*/ Telephone/Fax/Email	Immediately** Vendor SAE Portal*/ Telephone/Fax	Within 24 hours** Vendor SAE Portal*/ Telephone/Fax/Email	Prompt notification required no later than 48 hours** Update Vendor SAE Portal
Written	Within 48 hours** Vendor SAE Portal	Within 48 hours** Vendor SAE Portal	

*If the SAE Portal is not available, alternative modes of communication must be used to report within the

specified time frames.

**The time period for notification of an SAE begins when the Investigator or any site personnel obtains knowledge of the event.

Institutional Review Board Notification

The Investigator must also promptly notify the IRB/REB of the SAE, including any follow-up information in accordance with local institutional policy.

If a given SAE is associated with the study medication and is unexpected, CASI Pharmaceuticals will forward an Investigational New Drug application (IND) Safety Report to the regulatory authorities and to the Investigator(s). In accordance with FDA regulations, it is the Investigator's responsibility to promptly inform the IRB/REB of the IND Safety Report.

Significant or Unexpected Toxicities

CASI Pharmaceuticals, the Medical Monitor, and the involved Investigator will monitor the safety experience of all patients treated. Significant or unexpected toxicities that, in the judgment of the Investigator, the Sponsor, or the Medical Monitor, presents an unacceptable consequence or risk to the patient will result in discontinuation of the patient from further study participation. The Investigator will notify CASI Pharmaceuticals immediately of any significant or unexpected toxicities. The Investigator, CASI Pharmaceuticals, or the Medical Monitor will notify other investigators and all institutional review committees of important or unexpected toxicity. Treatment may be delayed to allow recovery from treatment-related toxicities and to consider if dose reductions are appropriate for continued therapy with ENMD-2076. A delay of up to 3 weeks is allowed for patients to return to baseline or Grade 1 from any treatment-related side effect. Treatment delays for events such as intercurrent illnesses will be discussed with the Investigator and Medical Monitor to determine if a patient may remain on study if a delay of more than two weeks is required.

Post Study Adverse Events

Investigators are not obligated to actively seek information on AEs or SAEs in former study participants who completed the end of study visit. However, the Investigator should promptly notify CASI Pharmaceuticals, or designee, if the Investigator learns of any SAE or death of a study patient within 30 days after a patient has discontinued study drug administration, and such event(s) is (are) reasonably related to the study medication.

Investigators should promptly notify CASI Pharmaceuticals, or designee, if they become aware of a former study participant who is one of the parents of a subsequently conceived child with a congenital anomaly (see below).

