8.2 Secondary Efficacy Variables

- ∞ 6-month progression free survival (PSF6) rate
- ∞ The median PFS and TTP as based on RECIST 1.1 and measured by time from first study drug administration until progression or death.
- ∞ The median Overall survival as measured by time from first study drug administration to death or study completion.
- ∞ Safety data will be collected from time of informed consent through study completion /withdrawal up to 30 days after the last dose of study medication by each subject.

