8.3.6 Adverse Events

8.3.6.1 Adverse Events (AE) and Serious Adverse Events (SAE)

An adverse event (AE) is any untoward medical occurrence in a subject participating in a clinical trial. An adverse event can be any unfavorable and unintended sign, symptom or disease

temporally associated with the use of the study medication, whether or not considered related to the study medication. AEs will be collected from the start of treatment until 30 days following the final visit dose. Any events occurring prior to treatment will be recorded on the medical history page with the event name and onset date and end date if not continuing. Pre-existing, known clinically significant conditions observed at screening should be recorded as medical history.

This definition also includes accidental injuries, reasons for any change in medication (drug and/or dose) other than planned titration, reasons for admission to a hospital, or reasons for surgical procedures (unless for minor elective surgery for a pre-existing condition). It also includes adverse events commonly observed and adverse events anticipated based on the pharmacological effect of the study medication. Any new laboratory abnormality assessed as clinically significant by the Investigator must be recorded as an adverse event.

A treatment emergent adverse event is any adverse event occurring after start of study medication and within the time of residual drug effect, or a pre-treatment adverse event or pre-existing medical condition that worsens in intensity after start of study medication and within the time of residual drug effect.

Adverse events should be recorded as diagnoses, if available. If not, separate sign(s) and symptom(s) are recorded. One diagnosis/symptom should be entered per record.

Note that death is not an event, but the cause of death is. An exception is the event of sudden death of unknown cause. Note that hospitalization is not an event; however, the reason for hospitalization is. Procedures are not events; the reasons for conducting the procedures are. In general, only the reason for conducting the procedure will be captured as an adverse event. However, if deemed necessary by the Investigator, a procedure can be captured along with the reason for conducting the procedure.

An overdose or medication error is not an adverse event unless it is temporally associated with an unfavourable or unintended sign or symptom.

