8.3.6.2 Clinical Laboratory Abnormalities and Other Abnormal Assessments

It is the responsibility of the Investigator to assess the clinical significance of all abnormal laboratory values. The Investigator will exercise medical judgment in deciding whether abnormal laboratory values are clinically significant and represent AEs. In some cases, significant changes within the range of normal will require similar judgment by the Investigator.

If an abnormal laboratory value or assessment is clearly related to a medically defined diagnosis or syndrome, the diagnosis or syndrome will be recorded on the AE page, not the individual laboratory values. Clinically significant abnormal laboratory values should not be listed on the AE page of the eCRF, unless clinical signs or symptoms are present.

All clinically significant abnormal laboratory results or assessments will be followed until they return to normal or become stabilized (up to 30 days after end of study drug administration).

8.3.6.3 Procedures for Assessing, Recording, and Reporting Adverse Events and Serious Adverse Events

Throughout the duration of the study, the Investigator will closely monitor each subject for evidence of drug intolerance and for the development of clinical or laboratory evidence of adverse events. All adverse events (expected or unexpected) which occur during the course of the study, whether observed by the Investigator or by the subject, and whether or not thought to be drug-related, will be reported and followed until resolution or until they become stable.

The Investigator will evaluate AEs according to the following guidelines:

- ∞ **NCI CTCAE Version 4.0.** The Investigator must assign a CTC Grade for each AE ([Appendix A](#))
- ∞ **Description of event** (if the event consists of a cluster of signs and symptoms, a diagnosis must be recorded [e.g., flu syndrome] rather than each sign and symptom)

- ∞ **Onset Date**
- ∞ **Stop Date**
- ∞ **Seriousness** (see definition of SAEs, [Section 8.3.6.1](#))

The Investigator must record whether or not the AE meets the definition of serious. If the event is serious, the Investigator must complete a Serious Adverse Event report form (see [Section 8.3.6.4](#)). CASI Pharmaceuticals or designee will monitor the completeness and accuracy of these forms.

- ∞ **Relationship to Study Medication**

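### The Post Study Adverse Events paragraph limits 30-day SAE and death notification to related events, in conflict with the protocol's all-causality rules for the same 30 days

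*Combined protocol and SAP*

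**What the plan says.** The Post Study Adverse Events paragraph of Section 8.3.6.4 makes two statements.

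- On looking for events: "Investigators are not obligated to actively seek information on AEs or SAEs in former study participants who completed the end of study visit".
- On telling the sponsor: the investigator should notify promptly "if the Investigator learns of any SAE or death of a study patient within 30 days after a patient has discontinued study drug administration", with the added condition that "such event(s) is (are) reasonably related to the study medication". The two conditions are joined by an and, so both must hold.

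Other parts of the protocol address the same period.

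- Section 8.3.6.1 defines an adverse event as one "temporally associated with the use of the study medication, whether or not considered related to the study medication", and sets the collection window: "AEs will be collected from the start of treatment until 30 days following the final visit dose".
- Section 8.2, like the Synopsis, collects safety data "through study completion /withdrawal up to 30 days after the last dose of study medication by each subject".
- Section 8.3.6.3 says that all adverse events during the study, "whether or not thought to be drug-related, will be reported and followed until resolution or until they become stable".
- The Sponsor Notification part of Section 8.3.6.4 requires any SAE after the start of dosing to be reported and gives no end date. It covers non-fatal SAEs "regardless of expectedness or causality" and lists fatal and life-threatening ones with no condition.
- Section 8.3.6.5 requires any postmortem findings for a death within 30 days of stopping drug, again with no relatedness condition.

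**The concern.** Two rules with different causality conditions apply to the same events. A site holding an SAE that it considers unrelated, two weeks after the last dose, finds a general rule telling it to report and a paragraph written for the post-treatment period that asks for notice of related events only. It would be reasonable to follow the more specific text.

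Safety is a secondary objective, and Section 10.5.1 summarises the incidence of adverse events and SAEs. There is no control arm to help judge whether an event is due to drug or disease. Events close to progression are easily put down to the cancer, yet Section 4.3.1 lists elevated liver function tests, cholecystitis and gastrointestinal bleeding among the SAEs already seen with this drug. A causality filter applied site by site would therefore act where attribution is hardest. It would also work against the reason Section 8.3.6.4 gives for prompt SAE reports, which is that the Medical Monitor can see changes in the nature, severity or frequency of events.

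**Working it through.** The plan states no figure on this point that could be reproduced. The check sets the rules side by side.

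**Step 1: is it the same window?** The Post Study paragraph counts 30 days from stopping drug. Section 8.2 counts 30 days from the last dose. Section 8.3.6.1 is worded awkwardly, but I read it as 30 days from the final dose, in line with Section 8.2. All three describe essentially the same period.

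**Step 2: what does each rule require for one event?** Take an SAE on day 15 after the last dose, known to the site and judged unrelated.

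| Rule | Requirement |
|---|---|
| 8.3.6.1 and 8.2 | Collected: inside 30 days, causality irrelevant |
| 8.3.6.3 | Reported and followed, causality irrelevant |
| 8.3.6.4, Sponsor Notification and Table 3 | Reported: immediately if fatal or life-threatening, otherwise within 24 hours |
| 8.3.6.5 | If fatal, any postmortem findings go to the sponsor |
| 8.3.6.4, Post Study | No notice requested, because it is not judged related |

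The last row conflicts with every other row.

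**Step 3: what if the site does not know of the event?** Section 8.3.6.1 expects it to be collected. The Post Study paragraph removes the duty to ask once the end-of-study visit is complete. That visit is not defined. The nearest match is the End of Study Drug Administration visit of Section 9.1.4, shown as the discontinuation column of Table 4. Footnote l places those procedures at progression or at withdrawal for another reason, so the visit can come before most of the 30 days.

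**Step 4: does a later contact fill the gap?** After the discontinuation visit, Table 4 provides:

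- calls every three months to confirm survival (footnote p), which are not adverse event checks and are spaced more widely than 30 days;
- for patients who stop without progression, a CT scan every two months (footnote l). A scan may happen to fall inside the 30 days, but it is not an adverse event assessment.

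A patient who stops at progression has no scheduled safety contact in the window.

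**Step 5: what is one missed patient worth?** With 29 treated patients, 1/29 = 3.4 percentage points of incidence. If the trial stops after the first stage with 16 patients, 1/16 = 6.25 points. These are weights per patient, not estimates of how many would be missed.

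**The case against.** The strongest defence is that the reporting duty exists and is mandatory. The Sponsor Notification text says any SAE after first dose must be reported; the Post Study paragraph says only that the investigator should notify, and never says that unrelated SAEs are exempt. This stands. A reader might infer that the plan reports SAEs in the final 30 days only when they are judged related, or that the sponsor chose such a filter. The documents do not support either: every other relevant section points to all-causality reporting, and the stray text is one paragraph.

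A second defence is that other provisions reach into the window. Section 8.3.6.3 records AE outcome at a discontinuation status that includes the 30 days after the last dose. Section 8.3.6.2 follows clinically significant abnormal results for up to 30 days after drug. Section 6.1 follows all patients for safety and survival. Table 4 has the CT contacts, and patients are told to call with symptoms while on study (footnote h). This also stands, so a reader should not conclude that nothing captures those 30 days. What is missing is narrower: a scheduled adverse event contact within them.

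A third defence is that the paragraph concerns former participants, and a patient may not be one until the 30 days have passed. That could limit the no-seeking sentence, since the visit that triggers it is undated. It does not rescue the notification sentence, whose own terms place it inside the 30 days.

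**Conclusion.** The conflict is real and the Post Study paragraph is wrong as written. It sets a relatedness condition and removes the duty to ask, over a period that the rest of the protocol treats as all-causality.

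The harm is conditional. It arises only if sites follow this paragraph over Sections 8.3.6.1 and 8.3.6.3 and the Sponsor Notification text, or if the end-of-study visit comes early and events are then not sought. In the first case the events lost are those labelled unrelated. In the second, any event the site does not hear of could be missed. Either way the all-causality AE and SAE counts of Section 10.5.1 would be too low for the last 30 days, and the sponsor would learn of the events late or not at all.

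The size is unknown. A reader might want to multiply an assumed event rate by 29, but the documents give no rate for this window, and the Sponsor Notification rule covers the same events, so such a product would not count events outside the plan's rules. Deaths should still reach the survival analysis through the three-monthly calls, and the primary response-rate analysis is untouched.

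**What to change.** Reconcile the Post Study Adverse Events paragraph with Section 8.3.6.1, the Sponsor Notification text of Section 8.3.6.4, and Section 8.3.6.5.

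1. Require notification of every SAE and death through 30 days after the last dose, whatever the causality.
2. Apply the relatedness limit and the no-active-seeking sentence only after day 30.
3. State when the end-of-study visit takes place relative to the last dose.
4. State, with an entry in Table 4, that AE status is checked at about day 30 after the last dose. A phone call is enough.

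Possible wording for the paragraph: *All SAEs and deaths up to 30 days after the last dose are reported under Sponsor Notification irrespective of causality, and AE status is checked at about day 30. After day 30 investigators need not look for events, but should report any SAE they learn of that they consider related to study drug.*

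The cost is a short text edit and at most one call per patient, so no more than 29 calls. No eligibility, dosing or efficacy provision changes.

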8.3.6.5 Follow-up of Adverse Events and Serious Adverse Events and Other Investigations

All SAEs must be followed until they are resolved (return to normal or baseline values), stabilized, or the patient is lost to follow-up and cannot be contacted. Supplemental measurements and/or evaluations may be necessary to fully investigate the nature and/or

causality of an AE or SAE. This may include additional laboratory tests, diagnostic procedures, or consultation with other healthcare professionals. If the patient dies during the study or within 30 days following the End of Study Drug Administration/Discontinuation, any postmortem findings (including histopathology) must be provided to CASI Pharmaceuticals, or designee. CRF data should be updated with any new information as appropriate.

8.3.7 Pregnancy Information

A serum pregnancy test will be performed on females to determine pregnancy status at the time points outlined in [Table 4](#). If any female patient becomes pregnant while enrolled in the clinical trial, she will be withdrawn immediately. Any dispensed study medication must be returned to the clinical site. The Investigator must notify CASI Pharmaceuticals or designee by telephone within 24 hours of learning about the pregnancy. The Investigator must diligently follow the patient until delivery or termination of the pregnancy, providing necessary updated information to CASI Pharmaceuticals or designee. Generally, follow-up will occur within six to eight weeks following the estimated delivery date. Any premature termination of the pregnancy will also be reported.

Although pregnancy occurring in a clinical trial is not considered to be an AE or SAE, any pregnancy complication or elective termination of a pregnancy for medical reasons will be recorded as an AE or SAE and will be followed as such. A spontaneous abortion is always considered to be an SAE.

9. STUDY PROCEDURES AND FLOW CHART

A brief description of the chronological flow of the study is provided in the following sections.

A detailed time and event schedule is provided in [Table 4](#). Time 0 is defined as the precise time of the first ENMD-2076 administration on Day 1. All other time points in this study are relative to these definitions.

Screening Period (Day -28 to Day 1):

Prior to the initiation of any protocol-specific screening assessments not generally performed as part of routine patient care; the patient must be given a complete explanation of the purpose and evaluations of the study. Subsequently, the patient must sign and receive a copy of an Informed Consent Form that was approved by the IRB. Once informed consent has been obtained, the eligibility of the patient will be determined, and Screening Period assessments will be performed.

Treatment Period (before dosing on Day 1 up to Day 28):

On Day 1 before the initiation of the treatment, patients will be evaluated and baseline values for the specific assessments will be obtained. Thereafter during the initial Treatment Period, patients will visit the clinic for evaluation of tolerability, safety, and efficacy. Evaluation visits will be scheduled as described in [Table 4](#).

Table 4 Schedule of Assessments

Measurement/Treatment	Screening	Baseline	Follow-up after study drug administration ^a					Subject Discontinuation ¹
	Days -28 to 1	Day 1 (prior to dose)	Cycle 1			Cycle 2	Cycle 3 +	
			Day 1	Day 8	Day 15	Day 1 (day 29)	Day 1 (of Cycle 3+)	
Inclusion/Exclusion	X	X						
Informed Consent and HIPAA Authorization	X							
Medical/Cancer History	X							
Echocardiogram or MUGA	X					X ^j	X ^j	X ^j
Physical Examination ^c	X	X ^b				X	X ⁱ	X
Vital Signs (HR, temp, RR, BP)	X	X ^b		X	X	X	X ⁱ	X
12-lead ECG	X	X ^b	X ^m			X ^m	X ^{m,n}	X
ECOG Performance Status	X	X ^b				X	X	X
RECIST Assessment	X						X ^k	X
Histological ^q or cytological evidence for diagnosis	X							
Archived specimens for biomarker analyses and genomic testing ^r	X							
Tumor Biopsy ^s for subsequent biomarker analyses	X						X	X
Retained Plasma Sample with biopsy ^t	X						X	X
Hematology ^c	X	X ^b		X	X	X	X	X
Clinical Chemistry ^c	X	X ^b		X	X	X	X	X
Coagulation Tests ^c	X	X ^b					X ^j	
TSH level	X	X ^b				X		
Urinalysis ^{c,d}	X	X ^b				X		X
Pregnancy Test ^e	X	X ^b				X		
Dispense ENMD-2076			X			X	X ⁱ	
Tumor Marker AFP ^f		X				X	X ^k	X
Ammonia		X				X	X ^k	X

CT ^g (or MRI) of chest, abdomen, pelvis	X						X ^g	X
AE Monitoring		X	X	X	X	X	X ⁱ	X
Concomitant Medications	X	X	X	X	X	X	X ⁱ	X
Follow-up Phone calls								X ^p
Retained Plasma Sample Pharmacokinetics ^o			X	X	X	X	X	

AE = adverse event; BP = blood pressure; DCE-MRI = dynamic contrast enhanced magnetic resonance imaging; HIPAA = Health Insurance Portability and Accountability Act; HR = heart rate; RR = respiratory rate; TSH = thyroid stimulating hormone.

- a. Each visit following Day 1 must be completed with ± 3 days of the indicated visit day and each monthly visit must be completed within ± 7 days of the indicated visit day.
- b. Repeated only if more than 72 hours since screening assessments.
- c. Specific tests are listed in the protocol.
- d. If a patient develops 2^+ proteinuria, then a 24-hour urine collection is required for quantification and a repeat urinalysis should occur every week until resolution.
- e. Women of childbearing potential only.
- f. Tumor markers need to be assessed within 3 days of Cycle 1 Day 1, on Cycle 2, Cycle 3, Cycle 5, etc, and at the end of treatment, but optional on even cycles after Cycle 2.
- g. Baseline scans must be done within 28 days prior to entering study and performed two months after Cycle 1 Day 1 and every two months after (\pm 7 days window). CT Scan can be either liver tri-phasic or liver 4-phase but should be consistent throughout the study.
- h. AEs and concomitant medications are monitored continually while on study. (Patients are instructed to call with AE symptoms between scheduled visits).
- i. Completed on Day 1 at each new cycle.
- j. Completed if clinically indicated and by discretion by the Investigator.
- k. Completed at Cycle 2 and every 2 cycles after baseline (ie. Day 1 of Cycle 3, Cycle 5, etc).
- l. These procedures should be done if a patient reaches disease progression (which may occur at a scheduled visit) or if a patient withdraws for other reasons. For subjects that withdraw for other reasons a CT scan is required every two months until disease progression or death.
- m. Electrocardiogram should be performed on Day 1 of each Cycle pre-dose and 4-6 hours post dose.
- n. For Cycle 4 and beyond, Electrocardiogram may be omitted if all previous ECGs have been clinically insignificant by investigator discretion.

- o.* Blood samples for pharmacokinetic analysis will be drawn and processed in all patients prior to dosing on Day 1, Day 8 and Day 15 of Cycle 1, and Day 1 of Cycle 2 and Cycle 3, respectively.
- p.* After subject discontinues, a follow-up call should be done every three months for confirming survival.
- q.* This review will be conducted by a pathologist at the participating site to confirm the diagnosis. If there is a discrepancy, a review of a different archived specimen if available (heterogeneity is common) and/or identify a liver pathologist at another site who can provide independent review.
- r.* Tissue for biomarker study and genomic testing:
 - For archived tissue, 10-12 slides or a tissue block should be provided;
 - For tissue biopsy, multiple strips that is sufficient for biomarker study and genomic testing should be provided;
 - The tissue should be shipped to Memorial Sloan Kettering Cancer Center for subsequent biomarker study.
- s.* Tumor Biopsy: Tumor biopsy (optional) baseline up to 30 days prior to initiation of dosing (if patient had a biopsy after any previous treatments, they would be exempt of this biopsy) and at the end of treatment Cycle 2 (or Day 1 of cycle 3) in line with the imaging for tumor measurement. An additional optional biopsy at the time of disease progression will be performed in patients who have complete response, partial response or stable disease for > 16 weeks.
Tumor biopsy for minor patients will only occur if medically indicated and not solely for research purposes. If available, a sample of tumor tissue from any surgical resection or biopsy during treatment or at time of progression will be requested for biomarker and genomic testing on this study. The biopsy after cycle 2 and the optional biopsy at completion of therapy only refers to patients 18 years of age or older.
- t.* Retained Plasma Sample with biopsy: At the same time the biopsy is performed, i.e. at baseline and at the end of treatment Cycle 2 (or Day 1 of cycle 3).

